18 STUDY DOCUMENTATION AND CASE REPORT FORM

For each subject enrolled, a CRF will be completed, reviewed, and signed by the Investigator.

19 STUDY MONITORING

CEBIS International will do study monitoring. CEBIS will generate appropriate Monitoring Reports, retained in the Trial Master File, for each visit performed.

20 QUALITY ASSURANCE AUDITS

The raw data generated during the study and the clinical study reports will be liable for inspection and quality audit for conformance to this protocol and all the governing SOPs by an auditor from the Quality Assurance Department of the Sponsor and Investigator.

21 CONFIDENTIALITY OF DATA

The data identifying each study subject by name will be kept confidential and will be accessible to the study personnel, Quality Assurance Auditor during audits and if necessary, to the Institutional Ethics Committee and various regulatory agencies.

22 ARCHIVES

A representative sample of the drug supplies used in the study will be retained at the Clinical Unit. All data generated in connection with this study, together with the original copy of this protocol and the clinical study report will be archived as per current versions of the applicable Standard Operating Procedures.

Version 1.0/Date: November 27th, 2023

23 PUBLICATION POLICY

Results obtained from this study are property of the Sponsor. In case of publication, the Investigators will be informed and will be free to cooperate as Authors.

24 DEVIATIONS

All protocol deviations will be appropriately reviewed and documented in the raw data and those, which will affect the integrity of the study, will be reported in the clinical study report. For other deviations their impact on the study will be described.

25 TERMINATION OF THE STUDY

The Sponsor reserves the right to discontinue the trial at any time. Reasons for this termination will be provided to the subjects. The Investigators reserve the right to discontinue the study for safety reasons at any time.

In case the study ends early, the Sponsor must immediately notify the Competent Authorities and Ethics Committee about closing the study, within 15 days after it was stopped, with the clear explanation of the causes and presenting any existent follow-up safety measurements taken.

26 ADVERSE EVENTS

Subjects will be informed to bring to the notice of the medical personnel any adverse events that may occur during their participation in the clinical study.

A physician, either at the site of investigation or at a specialized medical unit, will do treatment of any adverse events.

All adverse events and treatment administered will be recorded in the clinical study report.

Adverse events experienced by subjects will be reported as per the applicable standard operating

Version 1.0/Date: November 27th, 2023

procedures and followed until the events have subsided. The study may be suspended or terminated depending on the seriousness of the adverse effects.

26.1 Classification method for adverse events and serious adverse events

An **adverse event/experience** (AE) is any unwarranted medical occurrence in a patient. For the purposes of this document, this is intended to include any adverse event whether device related or not.

Adverse Event: Any untoward medical occurrence, unintended disease or injury or any untoward clinical signs (including an abnormal laboratory finding) in subjects, users, or other persons whether or not related to the investigational medic al device.

- NOTE 1: This includes events related to the investigational device or the comparator.
- NOTE 2: This includes events related to the procedures involved (any procedure in the clinical investigation plan).
- NOTE 3: For users or other persons this is restricted to events related to the investigational medical device.

Serious adverse event: adverse event that:

- a) led to death,
- b) led to serious deterioration in the health of the subject, that either resulted in:
 - 1) a life-threatening illness or injury, or
 - 2) a permanent impairment of a body structure or a body function, or
 - 3) in-patient or prolonged hospitalization, or
 - 4) medical or surgical intervention to prevent life-threatening illness or injury or permanent impairment to a body structure or a body function,
- c) led to foetal distress, foetal death or a congenital abnormality or birth defect.

Version 1.0/Date: November 27th, 2023

NOTE: Planned hospitalization for a pre-existing condition, or a procedure required by the CIP (Clinical Investigation Plan), without serious deterioration in health, is not considered a serious adverse event.

26.2 Adverse Events Reporting

All adverse events will be recorded on the case report forms provided; a description of the event, intensity, duration, any action (e.g., treatment and follow-up tests) and the outcome should be provided along with the investigator's assessment of the relationship to the trial treatment.

Discrete episodes of chronic conditions occurring during a study period will be reported as adverse events to assess changes in frequency or severity. Adverse events will be documented in terms of a medical diagnosis (es). When this is not possible, the adverse event will be documented in terms of signs and symptoms observed by the investigator or reported by the subject at each study visit. Pre-existing conditions or signs and/or symptoms (including any which are not recognized at study entry but are recognized during the study period) present in a subject prior to the start of the study will be recorded on the Medical History form within the subject's CRF.

26.3 Notification of Serious Adverse Events

Any adverse reaction or abnormal value in the laboratory exams that is defined as Serious Adverse Events (SAEs), and which occurs during this study, will be immediately communicated by the Investigator to Pharmaunion as sponsor of the clinical study using the e-mail address: [contact] & [contact] to take the necessary steps in reporting to the relevant authorities

27 ETHICAL CONSIDERATIONS

27.1 Basic Principles

The study will be conducted according to the current amended version of the Declaration of Helsinki (as per 64th WMA General Assembly, Fortaleza, Brazil, October 2013), and other applicable regulatory requirements and guidelines in EU.

Version 1.0/Date: November 27th, 2023

The investigator agrees when signing the protocol to adhere to the instructions and procedures described in it and thereby to adhere to the principles of ICH-Good Clinical Practice of the European Community.

27.2 Informed Consent

The Investigator will inform the subjects about the study through an oral presentation regarding the purpose, procedures that will be carried out, potential hazards and the rights of the subjects. All subjects will be required to understand and sign a consent form summarizing the discussion before study initiation and screening examination. The original copy of the informed consent form will be retained in the Investigator's Trial Master File.

28 ACCEPTANCE CRITERIA OF PROTOCOL DEVIATION

All protocol deviations will be appropriately reviewed and documented in the raw data and those, which will affect the integrity of the study, will be reported in the clinical study report. In addition, deviations from original pharmacokinetic and statistical evaluation plan will be justified in the clinical study report.

29 STATISTICAL METHODS

Continuous data will be summarized in terms of the mean, standard deviation (SD), median, minimum, maximum and number of observations, unless otherwise stated. The minimum and maximum will be reported to the same number of decimal places as the raw data recorded in the database. The mean and median will be reported to one more decimal place than the raw data recorded in the database. The SD will be reported to two more decimal places than the raw data recorded in the database. In general, the maximum number of decimal places reported shall be four for any summary statistic. Confidence intervals will be presented to one more decimal place than the raw data.

Version 1.0/Date: November 27th, 2023

Categorical data will be summarized in terms of the number of patients providing data at the relevant time point (n), frequency counts and percentages. Percentages will be presented to one decimal place. Percentages will not be presented for zero counts. Percentages will be calculated using N (number per treatment group or overall) as the denominator.

30 DEMOGRAPHICS

Demographics and baseline disease characteristics will be summarized by descriptive statistics.

Demographic data will include: gender, age, weight, height, blood pressure, pulse, temperature, respiration, BMI. Baseline disease characteristics will include: medical history and concomitant medication.

31 SAFETY ANALYSIS SET

The secondary objective of the study is to assess the safety of the Lactacol/Lactazak® used in patients with FGIDs (intestinal colic and bloating). The Safety Analysis Set (SAF) includes all subjects who received at least one dose of study treatment. Subjects will be analyzed according to the study treatment they received. The Safety Analysis Set will be used for all safety analyses. For each study treatment, numbers of AEs and incidence rates will be tabulated. An event that occurred one or more times on the date of, or after, randomization will contribute one observation to the numerator of the incidence rate. The denominator of the rate will comprise all randomized subjects exposed to the study treatment. If the intensity or seriousness of the AE changes, then the overall intensity or seriousness will be the maximum intensity or seriousness of the multiple occurrences.

Serious adverse events, AEs leading to death and AEs leading to withdrawal of subjects will be tabulated for each treatment group.

Version 1.0/Date: November 27th, 2023

32 EFFICACY ANALYSIS SET

- The primary endpoint of the study is to assess the clinical efficacy of the Lactacol/Lactazak® in alleviating the clinical symptomatology by reducing the baby crying due to colic during study period and reducing bloating
- Secondary endpoint of the study is evaluating effectiveness and safety by:
 - ✓ Change in mean number of hours of child sleep during 24 h, evaluated in a daily manner during study period through a journal
 - ✓ Change in mean number of hours of caregiver sleep during 24 h, evaluated in a daily manner during study period through a journal
 - ✓ Change in mean number of awakenings during night evaluated in a daily manner during study period through a journal
 - ✓ Number of Adverse events;
 - ✓ Number of participants withdrawn due to lack of tolerability

P values <0.05 will be considered statistically significant. Statistical analyses will be performed using IBM SPSS Statistics 20 for Windows.

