
1 CLINICAL STUDY PROTOCOL

Study Short Name	Open-Label, Prospective, Multicenter Study to Assess efficacy			
Study Short Ivaine				
	and safety of Lactacol/Lactazak ®, a food supplement, in			
	intestinal colic and bloating			
Tested products	Lactacol/Lactazak ®			
	 The food supplement "Lactacol Fiale" (Lactacol), whose notification dated 20 November 2023 is annexed hereto, has the same formula as the food supplement "Lactazak" (PRG 570/2023). (Annex 1) Lactacol Fiale and Lactazak are the same food supplement with 			
	different trade names			
Study purpose	To assess efficacy and safety of Lactacol/Lactazak ®			
Market Status of the Tested Products	Notified to Health Ministry - General Directorate of Hygiene,			
	Food safety and nutrition protection - 20 November 2023			
Study Design:	Open-label, multicenter, prospective, non-comparative, non-			
	interventional study			
Protocol number	CBSPH_CBS27112023			
Protocol version	1.0			
Protocol date	Novemver 27 th , 2023			
Sponsor	Pharmunion LLC,			
	[name]			
Manufacturer	SALIX S.R.L.			
	[name]			
	[name]			
CRO	CEBIS International SRL			
	[name]			

Version 1.0/Date: November 27th, 2023

Open-Label, Prospective, Multicenter Study to Assess effiCacy and safEty of Lactacol/Lactazak ®, a food supplement in *intestinal colic and bloating*

Open-label, multicenter, prospective, non-comparative, non-interventional study

Protocol code: CBSPH CBS12122022

Version 1.0/Date: November 27th, 2023

SHORT name: PACE Study

CONFIDENTIALITY STATEMENT

The information contained in this document, especially unpublished data, is the property of CEBIS International (or under its control), and therefore provided to you in confidence as a potential participant or participant of this epidemiological study, potential investigator or consultant, for review by you, your staff and an applicable Independent Ethics Committee/Institutional Review Board. It is understood that this information will not be disclosed to others without written authorization from CEBIS except to the extent necessary to obtain informed consent from those persons to whom the tests may be applicable.

Version 1.0/Date: November 27th, 2023

1. Study Synopsis

1	Protocol	CBSPH_CBS27222023
1	identification:	Version 1.0/Date: November 27 th , 2023
	Protocol title:	Open-Label, Prospective, Multicenter Study to Assess efficacy and

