		3. Change in mean number of awakenings during night evaluated in a daily manner during study period through a journal			
		Safety will be assessed though:			
		1. Number of Adverse events;			
		2. Number of participants withdrawn due to lack of tolerability			
12	Sample size	30			
	Statistical Methods	Continuous data will be summarized in terms of the mean, standard			
		deviation (SD), median, minimum, maximum and number of			
		observations, unless otherwise stated. The minimum and maximum			
		will be reported to the same number of decimal places as the raw data			
		recorded in the database. The mean and median will be reported to one			
		more decimal place than the raw data recorded in the database. The SD will be reported to two more decimal places than the raw data recorded			
		_			
13		in the database. In general, the maximum number of decimal places reported shall be four for any summary statistic. Confidence intervals will be presented to one more decimal place than the raw data.			
		Categorical data will be summarized in terms of the number of patients providing data at the relevant time point (n), frequency counts and			
		percentages. Percentages will be presented to one decimal place. Percentages will not be presented for zero counts. Percentages will be			
		calculated using N (number per treatment group or overall) as the denominator.			
		denominator.			
14	Eligibility	Inclusion Criteria:			
		• pediatric population 0-4 months;			

		• Established diagnosis: FGIDs (intestinal colic and bloating).	
		Signed Informed Consent for data collecting;	
		Exclusion Criteria:	
		Unwillingness to provide signed Informed Consent for data collecting;	
		 Patients participating in other trials 	
		Allergy to any of the product ingredients	
	Visits:	3 visits:	
15		 Visit 1 - Screening and enrollment visit; Visit 2 - Day 14 from Therapy initiation; Visit 3 - Phone Follow-up 	
16	Study procedure	This non-interventional study will be conducted in Bulgaria in routine clinical practice by GP, pediatricians, family doctors. Data will be collected prospectively. Lactacol/Lactazak® will be administered in accordance with approved leaflet. Patient demographic data would be collected during screening visit where available (e.g., age, gender, geographic location, Apgar score, type of birth method) All the assessments for primary and secondary objectives will be performed at baseline and periodically according to the national	

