8 BACKGROUND

The most prominent feature of Infant Colics is prolonged crying. Additional characteristics, including clenching of the fists and flexion of the hips, have led to the suggestion that these behaviors are related to abdominal discomfort; thus, the term "colic, "derived from kolikos, the Greek term for colon. Infant colic is challenging for new parents and is a reason for 10% to 20% of paediatrician visits during the early weeks of an infant's life. Colic is estimated at affecting 5% to 40% of infants worldwide. The condition typically presents in the second or third week of life, peaks around 6 weeks, and resolves by the age of 12 weeks in 60% of infants and by 16 weeks of age in 90%. Inconsolable crying, irritability, and screaming without an obvious cause characterize colic; during these episodes of fussiness, which occur more frequently in the evenings, the affected infant classically appears red-faced, draws up the legs and tenses up the abdomen. The traditional methods of soothing the infant often fail to relieve the infant's distress. First described in 1954, the original "Wessel's Rule of 3s" diagnostic criteria (symptoms lasting for 3 hours per day, 3 or more days per week, for 3 or more weeks, starting around 3 weeks of age), has undergone a transition in recent years. The Rome IV criteria describe colic in infants from birth to 5 months of age to make the definition of infantile colic more consistent for research purposes. The criteria are as follows:

- An infant who is <5 months of age when the symptoms start and stop
- Recurrent and prolonged periods of infant crying, fussing, or irritability reported by caregivers that occur without obvious cause and cannot be presented or resolved by caregivers
- No evidence of infant failure to thrive, fever, or illness

While benign and self-limiting, the condition is frustrating for parents and has been linked to maternal postpartum depression and shaken baby syndrome. Since treatments for colic are controversial and inconsistent, the role of the physician as a counsellor and educator to parents is critical. The several factors involved in the etiopathogenesis (food intolerance or allergy to cow's

Version 1.0/Date: November 27th, 2023

milk protein, intolerance to lactose, intestinal hyperperistalsis, neuro-hormonal immaturity, maternal anxiety and familial stress), make the management of infants with colics difficult.

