13 STUDY POPULATION

The investigators will enroll in this study 30 subjects accordingly to the inclusion and exclusion criteria.

STUDY TREATMENT

Paediatric patients will be enrolled after diagnosis with intestinal colic and bloating. They will be

treated with Lactacol/Lactazak ® as presented below:

Product: LACTAZAK, Route of administration: Oral route, Single dose: 0.5 ml (700 FCC

ALU). Maximum daily dose: 6 ml (8400 FCC ALU).

Method of administration: Prior to use, twist the cap and shake well, use a pipette to collect 0.5

ml of solution and give the baby before each breastfeeding or add to the milk formula for 14

consecutive days.

LACTAZAK is degraded, being exposure to high temperatures, so this enzyme should not be

added to hot food or liquid. Store at room temperature (up to 25°C), away from heat sources and

protected from light. Keep in the original packing. Keep out of the reach of children.

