16 OUTCOMES

Primary endpoint

Efficacy will be evaluated by:

- reducing the number of babies crying episodes per day due to colic's during study period
- bloating reduction assessed though 3-point Likert scale

Pharm

Protocol code: CBSPH_CBS27112023

Version 1.0/Date: November 27th, 2023

Secondary endpoint

Effectiveness will be evaluated through the collected responses during study period:

- 4. Change in mean number of hours of child sleep during 24 h, evaluated in a daily manner during study period through a journal
- 5. Change in mean number of hours of caregiver sleep during 24 h, evaluated in a daily manner during study period through a journal
- 6. Change in mean number of awakenings during night evaluated in a daily manner during study period through a journal

Safety will be assessed though:

- 3. Number of Adverse events;
- 4. Number of participants withdrawn due to lack of tolerability

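### Section 32 pairs a clinical-efficacy aim with P<0.05 in a single-arm study of a self-limiting condition; a significant before-after change in crying cannot be read as a product effect

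*Protocol*

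**What the plan says.** The title page describes an "Open-label, multicenter, prospective, non-comparative, non- interventional study". Section 13 fixes the size: "The investigators will enroll in this study 30 subjects accordingly to the inclusion and exclusion criteria". The synopsis in Section 1 admits a "pediatric population 0-4 months" with an established diagnosis of intestinal colic and bloating.

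Section 16 gives two primary endpoints: "reducing the number of babies crying episodes per day due to colic's during study period" and "bloating reduction assessed though 3-point Likert scale". Section 15 places assessments at baseline, Day 14 and Day 28 (by phone). The product is given for 14 days.

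Section 32 words the aim as efficacy: "The primary endpoint of the study is to assess the clinical efficacy of the Lactacol/Lactazak® in alleviating the clinical symptomatology". It closes with "P values <0.05 will be considered statistically significant". It names no test, null value, time point, external rate or performance goal. Section 29 covers descriptive summaries and rounding only.

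Section 8 calls colic benign and self-limiting, with onset in the second or third week of life, and says that it "peaks around 6 weeks, and resolves by the age of 12 weeks in 60% of infants and by 16 weeks of age in 90" per cent.

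**The concern.** With one arm, reduction endpoints and no external benchmark, any P value for the primary endpoints has to come from comparing follow-up with baseline, that is, from a null of zero change. Zero change is not what an untreated group would show if it follows the course in Section 8. Eligible ages span both the approach to the peak and most of the resolution, so the expected untreated change depends on how old the infants are at entry.

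What is at stake is the primary conclusion. Section 32 puts a significance threshold beside an efficacy aim, and Section 8 supplies the reason why crossing that threshold would not show efficacy. Nothing in the Protocol connects the two. The final choice of paired test, wherever it is made, cannot repair this, because no paired test supplies a comparator.

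**Working it through.** **The Protocol's own figure.** The sample size of 30 comes with no effect size, SD, power or sidedness, so it cannot be reproduced.

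**Step 1: Section 8 alone.** Let F(a) be the proportion resolved by age a: F(12) = 0.60 and F(16) = 0.90. For an infant still colicky at age a, the chance of untreated resolution within d weeks is

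(F(a+d) − F(a)) / (1 − F(a)).

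At 12 weeks, over 28 days: (0.90 − 0.60) / (1 − 0.60) = 0.75. This needs no further assumption.

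**Step 2: other ages.** Assumed: F = 0 at week 6, F = 1 at week 20, and straight lines between the known points.

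| Age at entry | Resolved by Day 14 | Resolved by Day 28 |
|---|---|---|
| 6 weeks | 20% | 40% |
| 8 weeks | (0.40 − 0.20)/0.80 = 25% | 50% |
| 10 weeks | (0.60 − 0.40)/0.60 = 33% | 58% |
| 12 weeks | (0.75 − 0.60)/0.40 = 37.5% | 75% |

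**Step 3: chance of P<0.05 in favour of an inert product, without modelling episode counts.** Take a two-sided exact sign test with n = 30; the cut-off is 21 of 30 improved. If a proportion p resolves and the rest are equally likely to go up or down, each infant improves with probability p + (1 − p)/2. With p = 0 the favourable-direction error is 2.1%. It is 18% at p = 20%, 26% at 25%, 43% at 33% and 53% at 37.5%.

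**Step 4: paired t-test on crying episodes at Day 14.** Assumed: 5 episodes a day falling to 1 on resolution, SD of other change 1.5-3, ages uniform within each range, no trend before week 6, n = 30, simulated.

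- Ages 4-12 weeks, SD 2: about 49%. Check by hand: mean resolution is about 24%, so mean change is −4 × 0.24 = −0.96. The variance is 2² + 16 × 0.24 × 0.76 = 6.92, so the SD is 2.63 and the standard error is 2.63/√30 = 0.48. The ratio of 2.0 sits almost on the critical value of 2.05, which gives roughly even odds.
- Age mixes from 3-9 to 6-14 weeks, SD 1.5-3: about 15-85%.
- All infants aged 2-6 weeks, SD 1.5-3: about 5-7%, against a nominal 2.5%.

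**Step 5: a different outcome model.** Assumed: coefficient of variation 0.3-0.7, within-infant correlation 0.3-0.5, crying either flat or rising 10% a week before week 6, and resolved infants set to zero episodes. Day 14 results in favour of an inert product are 17-62% for ages 3-12 weeks and 0-8% for ages 2-6 weeks. With the pre-peak rise, an inert product looks significantly *worse* in about 9-28% of trials at ages 2-6 weeks, and in 28-88% at ages 3-4 weeks.

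**Not covered.** Section 8 gives no natural history for bloating, so every figure here concerns crying. Regression to the mean after enrolment at a symptomatic moment, and unblinded caregiver reporting, are not modelled; both would be expected to add apparent improvement.

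**The case against.** The strongest reply is that this is openly a small, non-comparative, observational study. Section 32 only says when a P value counts as statistically significant. It names no test and no rule for declaring the objective met, and a statistical analysis plan may settle the test. That stands in part. A reader might infer that the Protocol lays down a success rule with a broken 5% error rate, under which an inert product would usually be declared effective. The text does not support that. The before-after test is inferred from the design, no decision rule is written, and the frequency of a favourable result depends on an age mix that nobody yet knows.

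Two further points stand. Day 28 gives larger figures (about 56-100% in the Step 4 model for the same age mixes), but it falls about two weeks after the 14-day product period and nothing makes it the primary time point, so Day 14 is the fairer basis. And apart from the 12-to-16-week figure, the magnitudes rest on assumed curve points, episode counts and SDs.

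What does not stand is that disclosing the single arm settles the matter. An explicitly descriptive study would need no efficacy wording tied to a significance threshold. Section 32 has both.

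**Conclusion.** The point holds as a limit on interpretation: for the crying endpoint, a significant change from baseline cannot support the efficacy aim in Section 32, whichever paired test is used. The 75% figure for 12-week-olds over 28 days follows directly from Section 8. The Day 14 range of about 15-85% for mixed ages, and about 5-7% for an all-young group, rests on linear resolution from week 6, a fall from 5 episodes to 1, an SD of change of 1.5-3 and n = 30. Confidence is high on the logic and moderate on the size.

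The width of the range is itself part of the finding. Before-after change is confounded by age at entry, mostly towards apparent benefit but possibly towards apparent harm in infants enrolled before the peak. No such statement can be made for bloating from this document.

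**What to change.** 1. In Section 32, state that P<0.05 denotes a change from baseline during product use and will not be concluded as efficacy.
2. Reword the primary objective (Sections 1 and 7) and the primary endpoint (Sections 1, 16 and 32) as change in crying episodes per day and change in bloating.
3. Report change by age at enrolment, or adjusted for it, and show the Section 8 resolution figures beside it as descriptive context only. Date of birth (Section 15) and age (Section 30) are already collected.

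Do not add a confirmatory test against a historical resolution curve. It would need a new endpoint and a definition of resolution that the Protocol lacks, would treat a partly assumed curve as a fixed null, and would leave regression to the mean and open-label reporting untouched.

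The cost is protocol wording and one age-based table or model, with no new infants or visits. The downside is a more modest claim.
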